8.5.7 Serious Adverse Event Reporting

Investigator Reporting of SAEs

All SAEs will be recorded on the appropriate SAE form and sent to DMID Pharmacovigilance Group (PVG). The SAE form will collect all relevant data concerning the SAE, including event term or description, date of study product administration, date of onset, duration or date of resolution, severity, seriousness, outcome, any action taken with the study product, and relationship to each study product or an alternate etiology as assessed by those with the training and authority to make a diagnosis and listed on the Form FDA 1572 (PI, co-investigator, licensed clinicians). In addition, the investigator should provide relevant MH, ConMeds, laboratory or diagnostic results, details of any treatment for the SAE, and a narrative including all other pertinent medical information.

Any AE that meets a protocol-defined serious criterion must be submitted immediately (within 24 hours of site awareness) on an SAE form to the DMID PVG via fax or email. SAEs reported via the SAE Hot Line must be followed with a fax or email submission:

DMID Pharmacovigilance Group
Clinical Research Operations and Management Support (CROMS)
[name]
[name]
SAE Hot Line: [name] (US) or [name] (outside US)
SAE [contact] (US) or [name] (outside US)
SAE Email Address: [contact]

In addition to the SAE form, select SAE data fields must also be entered into the SDCC system. Please see the protocol-specific MOP for details regarding this procedure.

Other supporting documentation of the event may be requested by the DMID PVG and should be provided as soon as possible.

At any time after completion of the study, if the site PI or appropriate sub-investigator becomes aware of an SAE that is suspected to be related to study product, the site PI or appropriate sub-investigator will report the event to the DMID PVG.

Regulatory Reporting of SUSARs

The sponsor will report any Suspected Unexpected Serious Adverse Reactions (SUSAR) to the FDA in an IND safety report. DMID will report an AE as a suspected unexpected adverse event only if there is evidence to suggest a causal relationship between the study intervention and the AE.

The Sponsor must ensure the event meets all three of the definitions:

1. Suspected adverse reaction.
2. Serious.
3. Unexpected.

Both seriousness and unexpectedness are important, but the event will be reported only if there is evidence to suggest a **causal relationship between the drug and the adverse event**, such as:

- A. A single occurrence of an event that is uncommon and known to be strongly associated with drug exposure.
- B. One or more occurrences of an event that is not commonly associated with drug exposure but is otherwise uncommon in the population exposed to the drug.
- C. On review as an aggregate analysis when the occurrence is higher than the historical control.

DMID will report to the FDA any unexpected fatal or life-threatening suspected adverse reaction as soon as possible, but in no case later than 7 calendar days after the sponsor's initial receipt of the information. If the event is not fatal or life-threatening the IND safety report will be submitted within 15 calendar days after the sponsor determines that the information qualifies for reporting as specified in 21 CFR Part 312.32. Relevant follow up information to an IND safety report will be submitted as soon as the information is available. Upon request from FDA, DMID will submit to the FDA any additional data or information that the agency deems necessary, as soon as possible, but in no case later than 15 calendar days after receiving the request. The DMID MM is responsible for determining whether a SAE is a SUSAR based on the nature, severity, or frequency of the event.

DMID will submit an IND safety report to the FDA and will notify all participating site PIs (i.e., all PIs to whom the sponsor is providing drug under its IND(s) or under any PI's IND(s) of potential serious risks from clinical studies or any other source, as soon as possible.

SAEs that are not SUSARs will be reported to the FDA at least annually in a summary format which includes all SAEs.

8.5.8 Reporting Events to Participants

Participants have the right to be informed of any new findings of AEs or SAEs that may affect their safety or influence their choice to participate or continue participating in the study. Any information provided to the participant will be blinded with respect to study treatment.

8.5.9 Adverse Events of Special Interest (AESI)

Definition of AESI

An AESI (serious or non-serious) is one of scientific and medical concern specific to the compound or program, for which ongoing monitoring and rapid communication by the investigator to the Sponsor may be appropriate. Such clinically significant events may require further investigation in order to characterize and understand them and will be collected as AESIs, discussed by the SMC, and expanded narratives of each written as indicated.

Protocol-defined AESIs are:

- All clinically significant cardiovascular Grade 3 or higher AEs including symptomatic cardiac arrhythmias and ECG abnormalities
- All clinically significant Grade 3 or higher gastrointestinal AEs
- Hepatic toxicity assessed by severe (Grade 3 or higher) based on values of liver function tests (LFTs)

All AESIs will be collected through study Day 28 and will be included in the safety analysis.

All AESIs are assessed for severity and relatedness to investigational product, recorded, and followed as described above under AEs and SAEs.

Reporting of AESI

All AESIs, whether serious or non-serious, also require additional reporting to the DMID PVG within 24 hours of site awareness for serious AESI or within 72 hours of site awareness for non-serious AESI. AESIs are reported on the appropriate CRF with additional reporting to DMID PVG using the protocol-approved SAE form. Submit AESI as follows:

DMID Pharmacovigilance Group
Clinical Research Operations and Management Support (CROMS)
[name]
[name]
SAE Hot Line: [name] (US) or [name] (outside US)
SAE [contact] (US) or [name] (outside US)
SAE Email Address: [contact]

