2.3 Risk/Benefit Assessment

2.3.1 Known Potential Risks

SLV213

Cathepsin inhibitors have been safely used in the clinic (Drake, Clarke et al. 2017; Fuchs, Meta et al. 2020).

Preclinical:

SLV213 is the oral formulation of the drug substance, K777. All preclinical development was conducted with K777 (K11777). The K777 toxicology program included single-dose and repeat-dose oral dose toxicity studies in rats and dogs. Pivotal studies included a 14-day GLP toxicity study in rats, a 28-day GLP toxicity study in dogs as well as standard GLP *in vitro* tests for genotoxicity. Non-GLP studies were also conducted in cynomolgus and rhesus monkeys. In general, K777 was well tolerated in all species after oral administration. The liver was identified as the target organ of toxicity. Reversible increases in transaminases (e.g., aspartate aminotransferase [AST], alanine aminotransferase [ALT]) were reported in all species at high doses. In the GLP 14-day rat toxicity study, the highest dose administered (150 mg/kg/day) produced mild effects on liver enzymes (2-fold elevation) that were not confirmed by histopathologic evaluation of the liver. In the 28-day GLP dog toxicity study, modest reversible elevations in serum transaminases were also observed. In addition, reversible microscopic changes were detected in the brain (100 mg/kg dose; females only) and in lymphoid tissues. These reversible changes were considered non-adverse due to lack of histopathologic, clinicopathologic, and clinical evidence suggestive of an organ or organismal functional impairment.

Modest depressions in food consumption and weight gain were also observed in several studies, but effects were reversible and not considered adverse. Emesis was frequently reported in the dog

at oral K777 doses ~100 mg/kg and was also reported after intravenous (IV) dosing in a recent dog safety pharmacology study. Changes in hematological parameters were not typically observed or not considered of toxicological significance. *In vitro* and *in vivo* GLP studies did not demonstrate genotoxic effects of K777.

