7. STUDY INTERVENTION DISCONTINUATION AND PARTICIPANT DISCONTINUATION/WITHDRAWAL

7.1 Halting Criteria and Discontinuation of Study Intervention

7.1.1 Study Halting Criteria

Cohort Halting Rules

If any of the following criteria occur, dosing of subsequent participants in the cohort will be halted and could resume after blinded review by the SMC at an *ad hoc* meeting:

- One participant experiences a treatment-related SAE assessed as related to the investigational study product, with the exception of accidental injury.
- One participant experiences a treatment-related Grade 3 or higher adverse event.
- Two or more participants experience a Grade 2 or higher systemic AE in the same higher level group term (HLGT) per MedDRA classification assessed as related to the study product.
- One participant develops QT prolongation on a post dose ECG, defined as a QT interval with Fridericia correction method (QTcF) > 500 msec (Grade 3).
- One participant develops clinically significant abnormal liver function tests as follows:
 - ALT and/or AST $> 5 \times$ upper limit of normal (ULN) in the absence of a total bilirubin increase.
 - ALT and/or AST elevations $> 3 \times$ ULN in the presence of a total bilirubin increase $> 2 \times$ ULN or an international normalized ratio (INR) > 1.5 without findings of cholestasis or other alternate etiology to explain the elevations (i.e., "Hy's Law cases").
 - Symptomatic ALT and/or AST elevations $> 3 \times$ ULN with the appearance of fatigue, nausea, vomiting, right upper quadrant pain or tenderness, fever, rash and/or eosinophilia ($> 5\%$ of total WBC count).

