Potassium increase – mmol/L	5.1 – 5.2	5.3 – 5.4	5.5 – 5.6	> 5.6
Potassium increase – mmol/L	3.5 – 3.6	3.3 – 3.4	3.1 – 3.2	< 3.1
Carbon Dioxide increase – mEq/L	32.1 – 36.0	36.1 – 40.0	> 40.0	Intervention indicated
Carbon Dioxide decrease – mEq/L	17.0 – 21.9	14.0 – 16.9	< 14.0	Metabolic acidosis Invention indicated
Calcium increase – mg/dL	10.5 – 11.0	11.1 – 11.5	11.6 – 12.0	> 12.0
Calcium decrease – mg/dL	8.0 – 8.4	7.5 – 7.9	7.0 – 7.4	< 7.0
Creatinine increase – mg/dL	1.50 – 1.79	1.80 – 2.00	2.01 – 2.50	> 2.50
BUN increase – mg/dL	23 – 26	27 – 31	> 31	Requires dialysis
Glucose (fasting) increase – mg/dL	100 - 110	111 - 125	>125	Insulin requirements or hyperosmolar coma
Glucose (fasting) decrease – mg/dL	65 – 69	55 – 64	45 – 54	< 45
Total Protein decrease – g/dL	5.5 – 6.0	5.0 – 5.4	< 5.0	--
Albumin decrease – g/dL	2.8 – 3.1	2.5 – 2.7	< 2.5	--
Total Bilirubin increase – mg/dL, when LFT  normal	1.5 – 2.1	2.2 – 2.7	2.8 – 4.2	> 4.2
Total Bilirubin increase – mg/dL, when LFT  increased	1.5 – 1.6	1.7 – 2.1	2.2 – 2.4	> 2.4
Alanine Aminotransferase (SPGT/ALT) increase – U/L, female male	44 – 100 60 – 137	101 – 200 138 – 275	201 – 400 276 – 550	> 400 > 500
Aspartate Aminotransferase (SGOT/AST) increase – U/L, female male	38 – 87 55 – 125	88 – 175 126 – 250	176 – 350 251 – 500	> 350 > 500
Alkaline Phosphatase (ALP) increase – U/L, female male	114 – 208 141 – 258	209 – 312 259 – 387	313 – 1040 388 – 1290	> 1040 > 1290
Amylase increase – U/L	110 – 150	151 – 200	201 – 500	> 500
Lipase increase – U/L	66 – 90	91 – 201	121 – 300	> 300
Magnesium decrease – mg/dL	1.30 – 1.50	1.10 – 1.29	0.90 – 1.09	< 0.90
Phosphorus (inorganic) decrease – mg/dL	2.3-2.5	2.0 – 2.2	1.6 – 1.9	< 1.6
Hematology				
Hemoglobin decrease – g/dL, female male	11.0 – 12.0 12.5 – 13.5	9.5 – 10.9 10.5 – 12.4	8.0 – 9.4 8.5 – 10.4	< 8.0 < 8.5
Hemoglobin decrease – g/dL,	Any decrease – 1.5	1.6 – 2.0	2.1 – 5.0	> 5.0

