**Table 8: Laboratory Adverse Event Grading Scale (continued)**

Parameter	Grade 1/Mild	Grade 2/Moderate	Grade 3/Severe	Grade 4/ Potentially Life-Threatening
change from baseline				
Platelets decrease – $\times 10^3/\mu\text{L}$	125 – 140	100 – 124	25 – 99	< 25
Leukocytes (WBC) increase – $\times 10^3/\mu\text{L}$	10.80 – 15.00	15.01 – 20.00	20.01 – 25.00	> 25.00
Leukocytes (WBC) decrease – $\times 10^3/\mu\text{L}$	2.50 – 3.50	1.50 – 2.49	1.00 – 1.49	< 1.00
Lymphocytes decrease – $\times 10^3/\mu\text{L}$	0.75 – 1.00	0.50 – 0.74	0.25 – 0.49	< 0.25
Monocytes increase – $\times 10^3/\mu\text{L}$	1.01 – 2.00	2.01 – 3.00	> 3.00	Intervention indicated
Basophils increase – $\times 10^3/\mu\text{L}$	0.16 – 0.50	0.51 – 0.80	> 0.80	Intervention indicated
Eosinophils increase – $\times 10^3/\mu\text{L}$	0.65 – 1.50	1.51 – 5.00	> 5.0	Hyper-eosinophilic
Neutrophils decrease – $\times 10^3/\mu\text{L}$	1.50 – 2.00	1.00 – 1.49	0.50 – 0.99	< 0.50
Coagulation				
Prothrombin Time – sec	11.2 – 12.3	12.4 – 13.4	13.5 – 14.0	> 14.0
Activated Partial Thromboplastin Time (aPTT) – sec	35.0 – 42.0	42.1 – 49.0	49.1 – 52.5	> 52.5
Urine Dipstick				
Nitrite	1+	2+	>2+	--
Urine Protein	Trace	1+	2+	Hospitalization or dialysis
Urine Glucose	Trace	1+	2+	Hospitalization for hyperglycemia
Urine Microscopy				
White blood cells (WBC) per HPF	0 – 10	11 – 50	> 50 or gross	Hospitalization or intervention
Red blood cells (RBC) per HPF	1 – 10	11 – 50	> 50 or gross	Hospitalization or packed red blood cells (PRBC) transfusion
Bacteria (microscopic)	Few	Moderate	Many	Hospitalization or intervention

 Liver function tests (LFT) include ALT and AST. Urine microscopy was only performed if urine dipstick was abnormal for blood, protein, glucose, and nitrites. The results of the urine microscopy would supersede the results of the urine dipstick.

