## 14.4 Safety Data

### 14.4.1 Displays of Adverse Events

**Table 22: Overall Summary of Adverse Events, Safety Population**

[**Implementation Note:** An “adverse event” includes laboratory AEs, ECG AEs, TEAEs, and other unsolicited AEs.]

Participants a with	400 mg SLV213 (N=X)		Placebo (N=X)		All Participants (N=X)	
	n	%	n	%	n	%
At least one adverse event	x	xx	x	xx	x	xx
At least one related adverse event	x	xx	x	xx	x	xx
Mild (Grade 1)	x	xx	x	xx	x	xx
Moderate (Grade 2)	x	xx	x	xx	x	xx
Severe (Grade 3)	x	xx	x	xx	x	xx
At least one severe (Grade 3) adverse event	x	xx	x	xx	x	xx
Related	x	xx	x	xx	x	xx
Unrelated	x	xx	x	xx	x	xx
At least one serious adverse event b	x	xx	x	xx	x	xx
At least one related, serious adverse event	x	xx	x	xx	x	xx
At least one adverse event leading to early termination c	x	xx	x	xx	x	xx
At least one adverse event of special interest						
At least one medically attended adverse event	x	xx	x	xx	x	xx
At least one unanticipated problem						

Note: N = Number of participants in the Safety Population.

a Participants are counted once for each category regardless of the number of events.

b Refer to Listing of Serious Adverse Events.

c As reported on the Adverse Event eCRF.

**Table 23: Serious Adverse Events and Adverse Events by MedDRA System Organ Class and Preferred Term, and Treatment Group, Safety Population**

[**Implementation Note:** If there is only one PT within a given SOC, then “Any PT” row will be omitted. An “adverse event” includes laboratory AEs, ECG AEs, TEAEs, and other unsolicited AEs. Serious adverse events will be displayed regardless of percentage of participants.]

MedDRA System Organ Class	MedDRA Preferred Term	400 mg SLV213 (N=X)			Placebo (N=X)			All Participants (N=X)		
		n	%	Events	n	%	Events	n	%	Events
Serious Adverse Events										
Any SOC	Any PT	x	xx	x	x	xx	x	x	xx	x
[SOC 1]	Any SOC	x	xx	x	x	xx	x	x	xx	x
	[PT 1]	x	xx	x	x	xx	x	x	xx	x
	[PT 2]	x	xx	x	x	xx	x	x	xx	x
	...									
[SOC 2]	Any SOC	x	xx	x	x	xx	x	x	xx	x
	[PT 1]	x	xx	x	x	xx	x	x	xx	x
...	...	x	xx	x	x	xx	x	x	xx	x
[Repeat for Other (non-serious) Adverse Events]										
Note: N = Number of participants in the Safety Population (number of participants at risk). n = Number of participants reporting event. Events = Total frequency of events reported.										

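### A liver event with ALT/AST between about 3 and 5 times ULN can halt the cohort under Protocol 7.1.1 and still not count as a hepatic AESI under Protocol 8.5.9

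*Protocol*

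**What the plan says.** - Protocol 2.3.1, on the preclinical programme: "The liver was identified as the target organ of toxicity".
- Protocol 8.5.9 defines the hepatic AESI as "Hepatic toxicity assessed by severe (Grade 3 or higher) based on values of liver function tests (LFTs"). AESIs go to pharmacovigilance within 24 hours if serious and 72 hours if not. They are also discussed by the SMC and given narratives as indicated.
- SAP Table 22 has one AESI row, "At least one adverse event of special interest". SAP Table 28 lists the events.
- Protocol 7.1.1 halts a cohort when one participant shows any of three liver patterns:
  - A: ALT and/or AST above 5 x ULN "in the absence of a total bilirubin increase".
  - B: ALT and/or AST above 3 x ULN with total bilirubin above 2 x ULN or INR above 1.5, "without findings of cholestasis or other alternate etiology to explain the elevations".
  - C: symptomatic ALT and/or AST above 3 x ULN, "with the appearance of fatigue, nausea, vomiting, right upper quadrant pain or tenderness, fever, rash and/or eosinophilia".
- SAP Table 8 grades ALT and AST in U/L. The Grade 2 range for ALT is "101 – 200 138 – 275" (female, male).
- LFT is worded in two ways. Inclusion criterion 4 Note 1, in both documents, lists transaminases, alkaline phosphatase and total and direct bilirubin. Footnote 1 to SAP Table 8 says "Liver function tests (LFT) include ALT and AST".
- SAP 4.5.1 collects INR without grading it. Prothrombin time is graded.

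**The concern.** The halting rule uses multiples of ULN and combinations of findings. The AESI definition uses the toxicity grade of single LFT values. If the lower halting multiple falls within Grade 2, a liver event serious enough to stop dosing may not be a hepatic AESI, for the organ the protocol names as the target of toxicity. Such a case would be missing from the AESI row of SAP Table 22 and from SAP Table 28. If non-serious, it would not trigger the 72-hour AESI report. In the symptomatic pattern, Grade 2 transaminases would not enter the Grade 3 laboratory row of the tolerability table (SAP Table 14) either.

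No planned table shows the pattern directly. SAP Table 33 presents chemistry parameters one at a time by grade, and SAP Table 35 covers prothrombin time and aPTT but not INR. Neither uses multiples of ULN or combines ALT/AST with bilirubin or INR.

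**Working it through.** **Inputs (SAP Table 8, U/L)**

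| Test | Grade 1 starts | Grade 2 | Grade 3 starts |
|---|---|---|---|
| ALT female | 44 | 101–200 | 201 |
| ALT male | 60 | 138–275 | 276 |
| AST female | 38 | 88–175 | 176 |
| AST male | 55 | 126–250 | 251 |

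Protocol 8.1.2 places the reference ranges in the MOP, so ULN has to be inferred. Two ways, in the row order above:

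- (a) Top of Grade 2 divided by 5: 200/5 = 40, 275/5 = 55, 175/5 = 35, 250/5 = 50. With these values all four rows share the same cut-points to rounding: Grade 1 starts near 1.1 x ULN, Grade 1 ends near 2.5 x, Grade 2 ends at 5 x and Grade 3 ends at 10 x.
- (b) Largest whole number below Grade 1: 43, 59, 37, 54.

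**Step 1: grade at 3 x ULN.** Under (a), 3 x ULN = 120, 165, 105, 150. Under (b), it is 129, 177, 111, 162. Values just above these are Grade 2 in every row. This holds for any ULN of 34–43, 46–59, 29–37 and 42–54 respectively. A lower ULN would give Grade 1, which is still not Grade 3.

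**Step 2: top of the Grade 2 band.** Under (a) it is 5 x ULN. Under (b) it is 200/43 = 4.65, 275/59 = 4.66, 175/37 = 4.73 and 250/54 = 4.63. If the laboratory's ULN is below (a), the band runs past 5 x; for example, a female ALT ULN of 34 gives 200/34 = 5.9. Capture of everything above 5 x ULN therefore assumes a ULN at least as large as (a).

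**Step 3: bilirubin limb of B.** Table 8 has a separate row for total bilirubin when ALT/AST are raised: Grade 2 is 1.7–2.1, Grade 3 is 2.2–2.4 and Grade 4 is above 2.4 mg/dL. The first one-decimal value above 2 x ULN grades as follows.

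| Bilirubin ULN (assumed, mg/dL) | First value above 2 x ULN | Grade |
|---|---|---|
| 1.0 | 2.1 | 2 |
| 1.1 | 2.3 | 3 |
| 1.2 | 2.5 | 4 |
| 1.3 | 2.7 | 4 |
| 1.4 | 2.9 | 4 |

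For a ULN of 1.1 or more, bilirubin itself is Grade 3 or 4, and the event is an AESI if bilirubin counts as an LFT.

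**Step 4: INR limb of B.** INR has no grade. Prothrombin time is Grade 3 from 13.5 s and Grade 4 above 14.0 s. Assume a sensitivity index near 1 and a mean normal time of 9.0–11.1 s (Grade 1 starts at 11.2 s). INR above 1.5 then means a time above 1.5 x 9.0 = 13.5 s to 1.5 x 11.1 = 16.7 s, probably Grade 3 or 4. A higher index could lower that grade. Neither LFT wording includes prothrombin time.

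**Result by pattern**

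| Protocol 7.1.1 pattern | Hepatic AESI under 8.5.9? |
|---|---|
| A, above 5 x ULN | Yes |
| B or C with ALT/AST above 5 x ULN | Yes |
| B, bilirubin limb, above 3 x to about 5 x | Yes if LFT includes bilirubin and its ULN is 1.1 or more; no if LFT is ALT and AST alone |
| B, INR limb, above 3 x to about 5 x | No, unless another LFT is Grade 3 |
| C, symptomatic, above 3 x to about 5 x | No, unless another LFT is Grade 3 |

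**The case against.** **All Hy's Law cases score zero.** A reader might infer this by taking the Table 8 footnote as the SAP's general definition of LFT. The documents do not support that. The footnote is attached to the two total bilirubin rows, where it tells the reader which tests select the row. Criterion 4 lists bilirubin under LFT, and Protocol 7.1.1 places the bilirubin and INR patterns under abnormal liver function tests. The bilirubin limb is normally caught. What stands is that 8.5.9 does not say which wording governs.

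**INR.** A case with INR above 1.5 would probably appear as severe or worse prothrombin time in SAP Table 35, and so in the Grade 3 laboratory row of Table 14. That makes it visible, but not a hepatic AESI under either LFT wording.

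**The case disappears.** It does not. It remains a graded TEAE, appears in SAP Table 27 if non-serious, shows in the laboratory listings, and goes to ad hoc SMC review through the halting rule. The SRC includes sponsor medical staff, and 24-hour reporting applies if the event is judged serious. What is lost is the AESI label, its row and its own report.

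**No contradiction.** Halting rules and AESIs serve different purposes, and other halting triggers, such as two related Grade 2 events in one HLGT, are not AESIs. This is fair: the two sections need not coincide. The point is that they use different scales for the target organ and no display links them.

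**Moot.** The SAP reports that the study stopped after Cohort 1, following two moderate allergic reactions. Rewording 8.5.9 cannot change reporting for cohorts never enrolled. The SAP displays for the abbreviated report are still relevant.

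**Conclusion.** The point holds in a limited form. With ALT/AST above 3 x and up to about 5 x ULN, the symptomatic pattern and the INR limb of Protocol 7.1.1 can halt the cohort without producing a hepatic AESI, unless another LFT reaches Grade 3. The bilirubin limb joins them only if LFT is read as ALT and AST alone, or if the bilirubin ULN is as low as 1.0 mg/dL and the value only just exceeds 2 x ULN. That the band just above 3 x ULN falls short of Grade 3 holds for any ULN below the Grade 1 floor of Table 8. Where the band ends, near 5 x, rests on the inferred ULNs.

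A reader might put a number on this: one missed case among 8 active participants turns 1/8 (12.5%, exact 95% CI 0.3–52.7%) into 0/8 (0–36.9%). The plan does not support that as a reported result. Table 22 has neither a hepatic row nor a confidence interval, the case is hypothetical, and the four replacement participants belong in the Safety Population once dosed, so the active denominator may lie anywhere from 8 to 8 + 4 = 12. The effect is on labelling and summary, and the right weight is a cheap improvement.

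**What to change.** - The sponsor should reconcile Protocol 7.1.1 with 8.5.9, and criterion 4 Note 1 with the SAP Table 8 footnote, and state which LFT wording governs the hepatic AESI. The halting thresholds stay as they are.
- In SAP 9.4, flag any participant who meets a 7.1.1 liver criterion alongside the AESI display in Tables 22 and 28, whether or not the event is an AESI.
- Add one Safety Population table by arm: number with maximum post-baseline ALT or AST above 3 x and above 5 x ULN, and how many of these had same-day bilirubin above 2 x ULN or INR above 1.5. Use the actual Safety Population denominator, including replacements.

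No new data are needed. Chemistry and coagulation are drawn on the same days (Protocol 8.3.2), and the laboratory listings already carry reference limits. SAP Section 15 allows an addendum before final data lock. The cost is one derived table and possibly one or two more flagged events.
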